12.2.2. Demography

For a given subject and a given demographic variable, a missing measurement will not be replaced.

Age: Age at the reference activity will be computed as the number of units (years, months, or days) between the date of birth and the reference activity.

12.2.3. Influenza vaccine exposure

For subjects who received more than one seasonal influenza vaccination during the study vaccination period, if any, only the first vaccination will be included in the analysis.

12.2.4. Safety

Subjects who did not report an adverse event will be considered as subjects who did not experience adverse event.

For the analysis of fever/pyrexia, all subjects with a fever/pyrexia Read code recorded will be considered as having fever/pyrexia regardless of what temperature had been recorded. For the analysis of fever >38.5C and 39.5C, all subjects with a fever/pyrexia Read code recorded within 7-day post vaccination and with a recorded temperature above the specified thresholds (>38.5C and >39.5C) within 7-day post vaccination, independent of route of measurement, will be considered as having fever above the specified thresholds.

The following process steps will be followed for the cleaning of temperature values:

- Every value recorded has a field for units, which can be left blank. If the units specified “Fahrenheit” or “F”, the value will be converted to Celsius, using this formula: $(\text{Value} - 32) * 5/9$.
- Otherwise, if the value is between 90 and 110, the value will be converted from Fahrenheit to Celsius, using the above formula.
- Otherwise, if the value is between 3.3 and 4.1, it'll be assumed a decimal place error, and the value will be multiplied by 10.
- Otherwise, if the value is between 330 and 410, it'll be assumed a decimal place error, and the value will be divided by 10.
- Otherwise, if the value is between 3300 and 4100, it'll be assumed a decimal place error, and the value will be divided by 100.

All temperature values below 37.5 or above 41.5 will be discarded.

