Gastrointestinal	Wheezing	Wheezing	1737..
	Decreased appetite	Loss of appetite	R0300
	Nausea	Nausea	198..
	Vomiting	Vomiting	199..
Fever/pyrexia	Diarrhoea	Diarrhoea	19F..
	Fever	Fever symptoms	165..
	Mild fever (<38.5° C rectal) High fever (>39.5°C)	O/E – Temperature level	2E3..
Sensitivity/anaphylaxis	Hypersensitivity reactions	Adverse drug reaction/Vaccine allergy	SN52..
	Anaphylactic reactions	Drug-induced anaphylaxis	SN501
	Facial oedema	Facial swelling	16J5..
	Local erythema	Erythema at injection site	SP3y5
Rash	Rash	Drug-induced rash	M130..
	Generalised rash	Rash	2I14..
	Local erythema	Erythema at injection site	SP3y5
General non-specific symptoms	Irritability	O/E - Irritable	225A..
	Drowsiness	Drowsiness	1B67..
	Fatigue	Fatigue	168..
Neurological	Peripheral tremor	Tremor	1B22..
	Guillain-Barre Syndrome (GBS)	Guillain-Barre Syndrome	F3700
	Seizure/ Febrile convulsions	Convulsion/Febrile convolution	1B64..
	Seizure/ Febrile convulsions	Convulsion/Febrile convolution	1B6B..
	Headache	Headache	1B1G..
Musculoskeletal	Muscle aches/ myalgia	Myalgia	N2410
	Arthropathy	Post-immunisation arthropathy	N037..

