In addition, weekly and cumulative incidence rates of any AEIs, each AEIs category (i.e. fever/pyrexia, local symptoms, any general non-specific symptom, any respiratory, any gastrointestinal, any sensitivity/anaphylaxis, rash, any musculoskeletal and any neurological AEs) and SAEs within 7 days post-vaccination period reported via ADR card will also be generated by Age group (6 months to 5 years; 6 to 12 years; 13 to 17 years; 18-65 years; >65 years) and by UK CMO-specified risk status (at risk, not at risk).

95% confidence interval (CI) adjusted for clustering effect of GP practices will be computed on all estimated incidence rates (Clopper-Pearson exact CI modified for cluster data as described in [Annex 1](#)).

The design effects and the intra-cluster correlation coefficients will also be estimated as described in [Annex 1](#) for the estimated cumulative incidence rates of AEIs reported on the ADR card within the 7 days post-vaccination period for the Cumulative vaccinated cohort Weeks 35-48 restricted to subjects who received the ADR card.

7.3.3. **Analyses of secondary objectives**

All analyses described for the primary objectives (refer to Section [7.3.2](#)) will also be generated by Vaccine group for all subjects included in the Weekly vaccinated cohorts and the Cumulative vaccinated cohorts (i.e. whether or not they received the ADR card).

For the weekly incidence rates (per 100 subjects):

- The denominator will be the number of subjects in the Weekly vaccinated cohort for the week of interest
- The numerator will be the number of subjects from the denominator who reported the specified AEI within 7 days following vaccination with the seasonal influenza vaccine using data entered in the EHR (i.e. AEIs derived from ADR card and medically attended AEIs)

For the cumulative incidence rates (per 100 subjects):

- The denominator will be the number of subjects in the Cumulative vaccinated cohort up to the week of interest
- The numerator will be the number of subjects from the denominator who reported the specified AEI within 7 days following vaccination with the seasonal influenza vaccine using data entered in the EHR (i.e. AEIs derived from ADR card and medically attended AEIs)

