7.3.7. Analysis on the RCGP RSC network of practices

The Royal College of General Practitioners Research and Surveillance Centre (RCGP RSC) network of practices includes approximately 170 GP practices.

The RCGP RSC network will be used to observe the trend of AEI rates using a larger sample of GPs.

The 2017 RSCGP RSC vaccinated cohort will include all subjects from the RSCGP RSC population

- who have not opted-out of data sharing
- who will be vaccinated against influenza at any point during the study vaccination period
- who have a valid NHS number recorded in EHR
- with date of birth recorded in EHR
- with gender recorded in EHR
- who are registered in EHR during the 7 days post vaccination period

The cumulative incidence rate (per 100 subjects) of each AEI within the 7 days post-vaccination period, with 95%CI, will be estimated by Vaccine group as follows:

- The denominator will be the number of subjects from the 2017 RCGP RSC vaccinated cohort
- The numerator will be the number of subjects from the denominator who reported the specified AEI during the 7 days following vaccination with the seasonal influenza vaccine using data entered in the EHR

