13. ANNEX 2 PREFERRED CODE LIST FOR ADVERSE EVENTS OF INTEREST

If a patient presents with adverse events post-vaccination (up to 7 days after), please code (ideally as a problem) as any of the following please code them into their computerised record

EMA surveillance condition	Read Code (5 Byte)	Read Code (CTV3)	Notes
Respiratory/Miscellaneous			
Conjunctivitis	F4C0.	XE16X	
Rhinorrhoea	1CB3.	XMO0h	
Nasal congestion	H1y1z	X77Gp	
Epistaxis	R047.	Xa96W	
Coryza	H00..	XEOX1	
Cough	171..	XMOCh	
Oropharyngeal pain	1922.	1922.	
	1CB3.	1CB3.	
Hoarseness	1CA2.	1CA2.	
Wheezing	1737.	XEOqs	
Gastrointestinal			
Decreased appetite	R0300	XMO7Y	
Nausea	198..	X75qw	
Vomiting	199..	XEOrA	
Diarrhoea	19F..	19F2.	
Fever/pyrexia			
Fever	163..	X76D1	
Mild fever (<38.5°C rectal)			Please include level of
Moderate fever (38.6-39.5°C)	2E3..	2E3..	temperature, to help us classify the fever
High fever (>39.5°C)			
Sensitivity/anaphylaxis			
Hypersensitivity reactions	SN52.	Xa5uf	
Anaphylactic reactions	SN301	X70vr	
Facial oedema	1E15.	Xe0ls	
Rash			
Rash	M130.	X50Ge	
Generalised rash	2114.	XMO7J	
General non-specific symptoms			
Irritability	225A.	225A.	
Drowsiness	1B67.	XMO6R	
Fatigue	168..	1682.	
Neurological			
Bell's palsy	F310.	F310.	
Peripheral tremor	1B22.	XEOrn	
Gullain-Barre Syndrome (GBS)	F3700	F3700	
Seizure/ Febrile convulsions	1B64.	XaDbE	
Headache	1B1G.	XMOCV	
Musculoskeletal			
Muscle aches/ myalgia	N2410	X75rs	
Arthropathy	N037.	X701f	
Local Symptoms			
Local erythema	SP3y4		
	SP3y5		
	SP3y6	X75ty	
	SP3y7		

N.B.: In coding these conditions there is no assumption about causation; this can only come from advanced analytics.

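### SAP 12.2.4 lets a normal temperature coded 2E3.. count as fever in the secondary EHR and RCGP RSC analyses; the effect is probably small in the enrolled practices and cheap to remove

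*SAP*

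**What the plan says.** **Case rule.** Under SAP 12.2.4, "all subjects with a fever/pyrexia Read code recorded will be considered as having fever/pyrexia regardless of what temperature had been recorded". The analyses of fever above 38.5°C and 39.5°C need a fever/pyrexia code and also a subject "with a recorded temperature above the specified thresholds".

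**Cleaning rule.** The same section corrects units and decimal places. For example, "if the value is between 90 and 110, the value will be converted from Fahrenheit to Celsius". It then closes with: "All temperature values below 37.5 or above 41.5 will be discarded".

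**Code list.** In SAP Annex 2 the Fever/pyrexia block holds a fever code and one further code, 2E3.., which serves the graded fever rows, including the one that begins "Moderate fever (38.6-39.5°C". The mild row has an upper limit and no lower limit. Practices are asked to add the temperature so that the fever can be classified. The code list in Protocol Appendix 7 describes 2E3.. as "O/E – Temperature level" and gives fever symptoms a separate code, 165...

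**Where the rule applies.** SAP section 7 refers all final analyses to Annex 1 for derivations. SAP 7.3.3 repeats on EHR data "All analyses described for the primary objectives", which include any-AEI and fever/pyrexia rates. SAP 7.3.7 plans, for the RCGP RSC network, "The cumulative incidence rate (per 100 subjects) of each AEI within the 7 days post-vaccination period". Neither section gives another fever rule.

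**The concern.** A code for a temperature reading can be attached to any reading, including a normal one. The case rule looks only at the code and sets the reading aside. The cleaning rule then removes a reading below 37.5 as a value but is silent on the code that carried it. A patient seen for a cough, with a normal temperature coded under 2E3.., would be tabulated as a fever.

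Fever is one of the expected reactions whose frequency the study exists to monitor. False cases would raise the any-fever rate in the secondary analysis and in the RSC analysis. They would raise the any-AEI rate only in the secondary analysis, and only for a subject with no other AEI. The Protocol synopsis says the final report will discuss the findings against RSC rates and, as appropriate, against the two earlier seasons, so differences in how often 2E3.. is used could also disturb those comparisons.

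**Working it through.** **1. Records traced through SAP 12.2.4** (no other fever-block code in the 7-day window; card code absent)

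| Entry | Value after correction | Value kept? | Any fever, as written | >38.5°C | Any fever, after the fix |
|---|---|---|---|---|---|
| 2E3.., 37.0 | 37.0 | no | yes | no | no |
| 2E3.., 98.6 | (98.6 − 32) × 5/9 = 37.0 | no | yes | no | no |
| 2E3.., 368 | 368/10 = 36.8 | no | yes | no | no |
| 2E3.., 37.5 | 37.5 | yes | yes | no | yes |
| 2E3.., 39.0 | 39.0 | yes | yes | yes | yes |
| 2E3.., no value | none | – | yes | no | yes |
| Fever-symptom code, no value | none | – | yes | no | yes |

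The Fahrenheit step runs from (90 − 32) × 5/9 = 32.2°C, and (99.5 − 32) × 5/9 = 37.5°C. Every entry from 90 to just under 99.5 is therefore converted, discarded as a value and still counted as fever. The graded column never changes.

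**2. Effect per subject.** With the 5,000 vaccinated subjects expected in SAP 3.1, each false case adds 1/5,000 = 0.02 per 100.

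**3. How many would matter.** The plan gives no figure for this point, so I first checked the interval method on Protocol Table 1. For 50/5,000, Clopper-Pearson gives 0.74% to 1.32% with a relative standard error of 14.1%; the table prints 0.7%, 1.3% and 14.1%. The table below gives the number of false cases that would lift the estimate above the upper limit belonging to the true count. The true rates are assumed; 1% is the event probability used in Protocol Table 2.

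| Assumed true rate | True cases | Upper 95% limit | Extra cases needed | Resulting estimate |
|---|---|---|---|---|
| 0.5% | 25 | 0.737% | 12 | 37/5,000 = 0.74% |
| 1% | 50 | 1.316% | 16 | 66/5,000 = 1.32% |
| 2% | 100 | 2.427% | 22 | 122/5,000 = 2.44% |

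The SAP's cluster-adjusted limits would generally be wider, so the counts would be larger.

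**4. How many are likely.** The only frequency evidence is the sample feedback sheet in Protocol Appendix 7. It shows 2 entries of 2E3.. and 9 of 165.. in one practice from 4 to 21 September 2015, which is 18 days. Temperatures are not shown.

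- Practice size (assumed for that practice): 5,000 to 7,034, the two figures in the Protocol's sample size section.
- Risk window: 8 days, from the SAP 7.3.2 footnote (day of vaccination plus 7). 5,000 × 8 = 40,000 person-days.
- Expected 2E3.. entries: 2/(7,034 × 18) × 40,000 = 0.6, up to 2/(5,000 × 18) × 40,000 = 0.9.
- With the Poisson 95% upper limit for 2 events, 7.2: 7.2/126,612 × 40,000 = 2.3, up to 7.2/90,000 × 40,000 = 3.2.

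These are entries at any temperature, febrile ones included. The scaling assumes that vaccinees have 2E3.. entries as often as all registered patients; they may consult more often.

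**The case against.** **2E3.. may be meant only to grade a fever.** Annex 2 gives fever its own code and asks for the temperature to classify it. If 2E3.. were itself a fever code, requiring a code as well as a value in the graded analyses would add little. This reading is possible, but 12.2.4 speaks of any fever/pyrexia code, Annex 2 lists 2E3.. in that block, and no text restricts it.

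**Discarding may mean dropping the entry.** A value below 37.5 can never exceed 38.5, so the floor does nothing in the graded analyses; perhaps it was meant to act on any-fever. But the sentence closes the steps for cleaning temperature values, and the case rule expressly sets the temperature aside.

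**Counting on codes is a deliberate, sensitive choice.** The Protocol accepts that meaning will be inferred from brief coded information, and the SAP takes a worst-case approach to missing AEI onset dates. That supports keeping fevers without a value. It does not support counting a measured normal temperature.

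**Changing the definition late may break comparability.** This stands and shapes the fix. The SAP is dated 11 December 2017. With reports due 3 weeks after each week, Week 46 (ending 19 November) was due on 10 December, so 12 of the 14 weekly reports were due before the SAP date.

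**The frequency is low.** This also stands for the enrolled practices, where Annex 2 asks for these codes when a patient presents with adverse events. A reader might infer a materially inflated fever rate; the illustrative 0.6 to 0.9 entries, against break-even counts of 12 to 22, do not support that. A reader might also infer that the RSC network is worse because SAP 3.3.1 asks only the 10 enrolled practices to use the preferred list. That is an inference about coding habits which the documents do not show.

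**Conclusion.** The defect holds on the wording: a stated rule classifies a measured normal temperature as fever when 2E3.. is the only fever-block code. It reaches the any-fever rate in the secondary and RSC analyses, and the secondary any-AEI rate in subjects with no other AEI. The graded analyses are protected because they need a qualifying value. The primary analysis is largely unaffected because the patient reports the event on the card.

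The size is unknown. In the 10 practices it is probably small, at about one 2E3.. entry of any temperature per 5,000 vaccinees. That rests on one 2015 sample sheet, an assumed practice size and equal coding in vaccinees. For the RSC network no estimate can be made. The weekly reports should not be assumed to be affected, since SAP 9.1.1 does not say that they use this derivation. This is a cheap improvement to the definition; it is not evidence that the fever results would mislead.

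**What to change.** In SAP 12.2.4, add one derivation rule. A subject is not counted as fever/pyrexia when the only fever-block code in the 7-day window is 2E3.. without the card code (9G4.. in Protocol Appendix 2) and every recorded value, after unit and decimal correction, is below the SAP's own 37.5 floor. Apply the test before values are discarded; otherwise a reading of 37.0 looks the same as no reading.

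Keep as fever all fever-symptom codes, card-reported fever, and 2E3.. entries with no usable value (none recorded, or above 41.5). The last group must stay because Annex 2 tells practices to use 2E3.. for mild, moderate and high fever. Show the as-written count as a sensitivity row in the secondary and RSC fever tables, so that comparison with the weekly reports and earlier-season rates is preserved.

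The cost is one sentence, one table row and a program edit, all on data already extracted. The downside is that 37.5 is a data-cleaning floor. A settled or treated fever coded only as 2E3.. with a lower value leaves the main count and appears only in the sensitivity row. So does an implausibly low entry that the corrections do not repair.

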12.3. Data presentation description

The following decimal description will be used for the analyses:

Display Table	Parameters	Number of decimal digits
Demographic characteristics, vaccine exposure	%	1
	Mean, median	1
	Standard deviation	1
Safety	%, LL & UL of CI	2

13. ANNEX 2 PREFERRED CODE LIST FOR ADVERSE EVENTS OF INTEREST

If a patient presents with adverse events post-vaccination (up to 7 days after), please code (ideally as a problem) as any of the following please code them into their computerised record

EMA surveillance condition	Read Code (5 Byte)	Read Code (CTV3)	Notes
Respiratory/Miscellaneous			
Conjunctivitis	F4C0.	XE16X	
Rhinorrhoea	1CB3.	XMO0h	
Nasal congestion	H1y1z	X77Gp	
Epistaxis	R047.	Xa96W	
Coryza	H00..	XEOX1	
Cough	171..	XMOCh	
Oropharyngeal pain	1922.	1922.	
	1CB3.	1CB3.	
Hoarseness	1CA2.	1CA2.	
Wheezing	1737.	XEOqs	
Gastrointestinal			
Decreased appetite	R0300	XMO7Y	
Nausea	198..	X75qw	
Vomiting	199..	XEOrA	
Diarrhoea	19F..	19F2.	
Fever/pyrexia			
Fever	163..	X76D1	
Mild fever (<38.5°C rectal)			Please include level of
Moderate fever (38.6-39.5°C)	2E3..	2E3..	temperature, to help us classify the fever
High fever (>39.5°C)			
Sensitivity/anaphylaxis			
Hypersensitivity reactions	SN52.	Xa5uf	
Anaphylactic reactions	SN301	X70vr	
Facial oedema	1E15.	Xe0ls	
Rash			
Rash	M130.	X50Ge	
Generalised rash	2114.	XMO7J	
General non-specific symptoms			
Irritability	225A.	225A.	
Drowsiness	1B67.	XMO6R	
Fatigue	168..	1682.	
Neurological			
Bell's palsy	F310.	F310.	
Peripheral tremor	1B22.	XEOrn	
Gullain-Barre Syndrome (GBS)	F3700	F3700	
Seizure/ Febrile convulsions	1B64.	XaDbE	
Headache	1B1G.	XMOCV	
Musculoskeletal			
Muscle aches/ myalgia	N2410	X75rs	
Arthropathy	N037.	X701f	
Local Symptoms			
Local erythema	SP3y4		
	SP3y5		
	SP3y6	X75ty	
	SP3y7		

N.B.: In coding these conditions there is no assumption about causation; this can only come from advanced analytics.

14. ANNEX 3 ADVERSE DRUG REACTIONS SOLICITED IN THE CARD

Possible side effect or Condition in the 7 days after influenza vaccination	Start date of the symptom	Please tick as appropriate
Conjunctivitis – Sticky eyes	____/17	
Runny nose	____/17	
Blocked nose	____/17	
Epistaxis – Nose bleed	____/17	
Common cold	____/17	
Cough	____/17	
Sore throat	____/17	
Hoarse voice	____/17	
Wheezing	____/17	
Decreased appetite	____/17	
Nausea – feeling sick	____/17	
Vomiting – being sick	____/17	
Diarrhoea	____/17	
Fever (add temperature if measured)	____/17	
Allergic reaction (rash)	____/17	
Other allergic reactions	____/17	
Facial oedema (swelling)	____/17	
Local reaction to vaccine	____/17	
Rash	____/17	
Irritability	____/17	
Drowsiness	____/17	
Fatigue	____/17	
Tremor / shaking	____/17	
Seizure / fits	____/17	
Headache	____/17	
Muscle aches	____/17	
Joint pain	____/17	
Other		
1. _____	____/17	
2. _____	____/17	
3. _____	____/17	
Add below if more		

15. ANNEX 4 ISO WEEKS

Table below presents the International Organization for Standardization (ISO) weeks 35 to 48 considered in the analysis (from 01SEP2017 to 30NOV2017):

Week	Week Starting - Ending
35	01/09/2017 - 03/09/2017
36	04/09/2017 - 10/09/2017
37	11/09/2017 - 17/09/2017
38	18/09/2017 - 24/09/2017
39	25/09/2017 - 01/10/2017
40	02/10/2017 - 08/10/2017
41	09/10/2017 - 15/10/2017
42	16/10/2017 - 22/10/2017
43	23/10/2017 - 29/10/2017
44	30/10/2017 - 05/11/2017
45	06/11/2017 - 12/11/2017
46	13/11/2017 - 19/11/2017
47	20/11/2017 - 26/11/2017
48	27/11/2017 - 30/11/2017
